4.1 Inclusion Criteria

- 1. Measured BMI of 35.0-55.0 kg/m² at time of screening.
- 2. 21-65 years of age (inclusive) at time of screening.
- 3. Failed attempt for a duration equal to 3-months at weight loss by alternative approaches (e.g. supervised or unsupervised diets, exercise, behavioral modification programs).
- 4. Stable weight (<3% change in self-reported weight) over the previous 3 months at time of screening).
- 5. Women of childbearing potential must agree to use at least one form of birth control (prescription hormonal contraceptives, diaphragm, IUD, condoms with or without spermicide, or voluntary abstinence) from time of study enrollment through study exit.
- 6. Willing and able to provide informed consent in English and comply with the protocol.

4.2 Exclusion Criteria

- 1. Previous abdominal surgery that significantly increases the medical risks of gastrostomy tube placement
- 2. Esophageal stricture, pseudo-obstruction, severe gastroparesis or gastric outlet obstruction, inflammatory bowel disease
- 3. History of refractory gastric ulcers
- 4. Ulcers, bleeding lesions, or tumors discovered during endoscopic examination.
- 5. History of radiation therapy to the chest or abdomen
- 6. Uncontrolled hypertension (blood pressure >160/100).
- 7. Diabetes treated with insulin or sulfonylurea medications
- 8. Any change in diabetes medication in previous 3 months
- 9. Hemoglobin A1C >9.5%
- 10. History or evidence of serious pulmonary or cardiovascular disease, including acute coronary syndrome, heart failure requiring medications, or NYHA (New York Heart Association) class III or IV heart failure (defined below):

Class III: patients with marked limitation of activity and who are comfortable only at rest

Class IV: patients who should be at complete rest, confined to bed or chair and who have discomfort with any physical activity

- 11. Coagulation disorders (platelets < 100,000, PT > 2 seconds above control or INR > 1.5)
- 12. Anemia (Hemoglobin <11.0 g/dL in women and <12.5 g/dL in men)
- 13. Liver enzymes (ALT and AST) ≥3.0 times the upper limit of normal
- 14. Thyroid Stimulating Hormone (TSH) >1.5 x upper limit of normal at screening.
- 15. Osteoporosis (DEXA T-Score \leq -2.5 standard deviations below normal peak values).
- 16. History of fragility fractures (fractures resulting from a fall from a standing height or less, or presenting in the absence of obvious trauma)
- 17. Pregnant or lactating
- 18. Diagnosed Bulimia or diagnosed Binge Eating Disorder (using DSM IV criteria)
- 19. Night Eating Syndrome (diagnosed by EDE)
- 20. Serum potassium < 3.8 mEq/L
- 21. Chronic abdominal pain that would potentially complicate the management of the device
- 22. Taking a GLP-1 agonist < 6 months.
- 23. Taking prescription or over-the-counter medications for weight loss in the last 3 months before screening, or planning to participate in a commercial weight loss program in the next 24 months. This includes taking medications for an unrelated medical condition which have been shown to result in weight loss such as Topiramate or Bupropion.
- 24. Taking medication once or more per week that causes weight gain (e.g. atypical antipsychotics, monoamine oxidase inhibitors, lithium, selected anticonvulsants, tamoxifen, glucocorticoids)
- 25. Self- reported history of substance abuse in last 3 years.
- 26. Malignancy in the last 5 years (except for non-melanoma skin cancer).
- 27. Physical or mental disability or psychological illness that could interfere with compliance with the therapy.
- 28. At high risk of having a medical complication from the endoscopic procedure or Aspiration Therapy weight loss program for any reason, including poor general health or severe organ dysfunction, such as cirrhosis or renal dysfunction (GFR <60 mL/min/1.73 m² at screening, calculated by using the Chronic Kidney Disease Epidemiology Collaboration (CKD-EPI) equation).

5.0 Study Procedures

5.1 Screening

After signing the Informed Consent Form, all potential subjects will complete the following screening procedure:

Subjects should fast for 12 hours overnight before this visit.

- Verification of subject eligibility according to all Inclusion and Exclusion Criteria.
- "Impact of Weight on Quality of Life" (IWQOL-Lite). This self-administered questionnaire is used to address specific areas of quality of life, including Physical Function, Self-Esteem, Sexual Life, Public Distress, and Work; takes approximately 10-15 minutes to complete. (See Appendix A)
- Questionnaire on Eating and Weight Patterns Revised (QEWP-R). This self-reported measure assesses binge eating, purging and other eating behaviors and takes approximately 10 minutes to complete. (See Appendix A)
- Eating Disorder Examination (EDE) version 12.0D⁵³. EDE is an interview-based assessment of disordered attitudes and behaviors related to eating, body-shape, and weight that also has items designed to diagnose eating disorders based on DSM-IV criteria. The psychometric properties of the measure are sound⁵⁴, and it is currently considered to be the best eating disorder assessment interview (Garner, 2002). The EDE will be administered by interviewers trained on interview administration and scoring. The EDE takes approximately 1 hour to complete.
- Screening interview to determine subject's ability to comply with Aspiration Therapy or Lifestyle Therapy and ensure subject fully understands all aspects of study involvement. (See **Appendix A**)
- Medical history
- Physical examination (including height, weight, and blood pressure outlined in **Appendix B**)
- Resting 12-lead electrocardiogram read locally by site physician
- Blood tests; a central lab will analyze samples for the following analytes:
 - o Complete Blood Count (CBC): hemoglobin, hematocrit, red blood cell count, white blood cell count and differential, mean corpuscular volume (MCV), mean corpuscular hemoglobin (MCH),

and mean corpuscular hemoglobin concentration (MCHC), platelet count

- PT, PTT (prothrombin time, partial thromboplastin time)
- o TSH
- Complete Metabolic Panel (CMP):glucose, calcium, sodium, potassium, chloride, BUN, creatinine, albumin, alkaline phosphatase, ALT, AST, bilirubin), plus magnesium
- Lipid panel (Total cholesterol, LDL-C, HDL-C, triglycerides)
- o Serum iron
- o Vitamin D 25-OH
- Hemoglobin A1C
- Urine pregnancy test in women of childbearing potential
- Urine protein dipstick
- Dual Energy X-Ray Absorptiometry (DEXA); Total body, hip and spine bone mineral density will be assessed by using DEXA to screen for osteoporosis. Osteoporosis is defined as a DEXA T-Score ≤ -2.5 standard deviations below normal peak values. Whole body, hip and spine scans will be performed annually throughout the study in subjects assigned to the Aspiration Therapy Group. Changes in bone mineral density in the AT Group will be compared to baseline values and with changes in bone mineral density reported in previous weight loss studies (historical controls).

5.2 Randomization

Eligible subjects who fulfill all enrollment criteria obtained during Screening will be randomized to the Treatment or Control Group in a 2:1 ratio, stratified by sex and BMI (< or ≥ 40.0 kg/m2) at each study site. A web-based randomization scheme will be established to ensure there is no possibility that group assignment can be known in advance. To avoid temporal bias, randomized blocks of varying sizes will be used to prevent investigators from having advanced knowledge of the assignment of the last subject in a given block. Randomization will occur within 14 days of the screening visit. Subjects will be notified by telephone of their group assignment.

5.3 Control Group

Subjects randomized to the Control Group will participate in 14 Medical & Study visits and a 10-session diet and behavioral education weight loss

program called "Lifestyle Therapy" (see **Appendix C**), which will be delivered to subjects over 52 weeks. These Lifestyle Therapy sessions may be given individually during the same visit as the Medical & Study visits or in a group with other subjects who are assigned to the Control Group.

Each individual Lifestyle Therapy session will last 20-30 minutes and group sessions, about 60 minutes; the sessions will be given at week 0, 2, 6, 10, 14, 20, 28, 36, 44, and 52.

Topics include includes nutritional, physical activity, and behavioral education topics. Subjects are instructed to follow a structured eating plan, which involves eating three meals a day, eating slowly and chewing food well, drinking plenty of fluids with each meal, and limiting snacking between meals. Physical activity topics include the health benefits of physical activity and strategies for increasing lifestyle activity. The behavioral program emphasizes strategies of self-monitoring and goal-setting, and includes problem-solving, dealing with high-risk situations / cues for unhealthy eating, and stress management.

All subjects will be asked to take a multivitamin and mineral supplement daily during the lifestyle intervention program.

The Medical & Study visits occur at weeks 0, 2, 6, 10, 14, 20, 24, 28, 32, 36, 40, 44, 48, and 52, as outlined in the study assessment schedule in **Table 3**.

All Medical & Study visits will include the following assessment and procedures:

- Body weight
- Blood pressure and temperature
- Presence of normal menses in women
- Adverse Events
- Concomitant medications
- Adherence with taking study-related medications (i.e. multivitamin supplement)
- Lifestyle Therapy (only at weeks 0, 2, 6, 10, 14, 20, 28, 36, 44, and 52)

Additional procedures and assessments are performed at visits as shown in **Table 3**:

- Blood tests
- Urine (dipstick) protein test

- Physical Examination
- EKG
- Eating Disorder Examination (EDE)
- DEXA
- Questionnaires (IWQOL, QEWP-R)

If a subject develops 2+proteinuria (100mg/dL) as measured by two successive dipstick analyses, random urine shall be collected to measure protein and creatinine to calculate protein to creatinine ratio.

For subjects who have diabetes, subjects will obtain a check (by fingerstick) of their fasting blood glucose every morning and a postprandial (2-3 hours after the evening meal) every evening for the first 6 weeks after starting AT, and report this blood glucose data to the study site every week by phone call, electronically, or during the study visit. Subjects will also be instructed to contact the research site immediately if their fasting blood glucose is <70 mg/dL or >200 mg/dL, or if their postprandial blood glucose is >400 mg/dL.

After the first 6 weeks, the protocol for home blood glucose monitoring will be determined by the study site physician. All changes in diabetes medications, based on changes in glycemic control, will be made in conjunction with the subject's private physician to ensure medical care is coordinated.

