2.1 Primary Efficacy Endpoints (52-week)

The first effectiveness primary endpoint is the mean percent excess weight loss (%EWL) at 52-weeks. The hypothesis for the first primary effectiveness endpoint is that the difference in the mean percent excess weight loss (%EWL) at 52-weeks for the Aspiration Therapy (AT) group and Control group is at least 10%. %EWL is defined as absolute weight loss divided by baseline excess weight and multiplied by 100. Excess weight will be determined from ideal body weights based on a BMI=25 kg/m².

The second effectiveness primary endpoint is that at least 50% of the AT group at 52-weeks realizes a %EWL \geq 25%.

Both primary endpoints must be met for the study to be considered a success.

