3.0 Study Design

This is a prospective randomized, active treatment controlled, parallel group, multi-center superiority trial of an endoscopically-placed device for weight loss. After the informed consent process, consent forms will be signed and dated, and all subjects who pass the screening process will be randomized in a 2:1 fashion to one of two groups for 52 weeks: AspireAssist plus Lifestyle Therapy ("AT Group") or Control Group (Lifestyle Therapy only). Lifestyle therapy involves treatment with a behavioral education weight loss program delivered as 10 individual or group sessions, in person or by webinar, over 52 weeks. It is, at the site's discretion, whether to provide (i) individual or group sessions or (ii) in-person or by webinar, but a site must provide the same therapy for all subjects. However, in the event, a site that has chosen group sessions are unable to schedule a patient for a group session, the site may provide an individual session for that patient. Aspiration Therapy involves percutaneous endoscopic placement of a gastrostomy device, which permits aspiration of a portion of gastric contents after meals, in addition to lifestyle therapy.

After 52 weeks, Control Group participation will end. The duration of therapy in the Control Group will end at 12 months because the number of drop-outs and rate of weight regain typically increases after 52 weeks of diet and behavioral therapy.

Subjects assigned to the AT Group will have the option to remain in the study for up to 4 more years for follow-up, provided they maintain a minimum of

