5.4.2.3 Day 14 Visit: Skin-Port Placement / Aspiration Initiation & Instruction

Approximately 14 days (no sooner than 10 days) after A-Tube placement, the subject shall return to the medical center for study assessments, Skin-Port

placement, and Aspiration Therapy training and initiation. The following assessments occur:

- · Body weight
- Blood pressure and temperature
- Stoma site healing
- Adverse Events
- Changes to medications
- Lifestyle Therapy
- Urine protein (dipstick)

The device installation is not considered complete until the Skin-PortTM is fastened to the A-Tube. This procedure is explained in detail in the AspireAssist Skin-Port Instruction for Use (**Appendix F**). Briefly, the ideal length of the Skin-Port from the belly is determined, the subject lies down, the A-Tube is cut and the Skin-Port snapped in place. The length of tube removed shall be recorded. The entire procedure takes about 10 minutes to perform. Once the A-Tube is converted to a low profile Skin-Port, the subjects are trained to: 1) aspirate gastric contents after meals by using the specialized CompanionTM aspiration device 2) maintain a clean A-Tube site, and 3) recognize signs and symptoms of potential A-Tube complications (see **Appendix I**).

Aspiration Therapy starts at the time the Skin-Port is fastened to the A-Tube. Subjects are instructed to consume a structured eating plan, which involves eating three meals a day, chewing food well, drinking a minimum of 16 ounces of non-caloric fluid with each meal, a minimum of 64 ounces of non-caloric fluid per day (including fluids ingested at meals) and limit snacking between meals. Subjects are also instructed to call their study team immediately if they are experiencing severe diarrhea or vomiting at any time with Aspiration Therapy to minimize the risk of fluid imbalances.

The aspiration procedure is performed approximately 20 minutes after finishing a meal and takes approximately 10 minutes to complete. The procedure involves connecting the Companion to the Skin-Port, which results in draining a portion of ingested food from the stomach (into a waste container or toilet), thereby preventing passage of food into the small intestine where food absorption occurs. Instructions for appropriate

aspiration of gastric contents are described in the AspireAssist User's Manual (Appendix H).

5.4.3 Phone Call at Week 0

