5.4.5 Medications

Subjects taking prescription or non-prescription medications related or unrelated to the study should take their medications at night before going to sleep, after aspirating, or at least 2 hours before aspirating gastric contents. If medications need to be taken with food, a snack should be consumed with the medication and not aspirated.

For subjects that have diabetes, subjects will obtain a check (by fingerstick) of their fasting blood glucose every morning and a postprandial (2-3 hours after the evening meal) every evening for the first 6 weeks after starting AT, and report this blood glucose data to the study site every week by phone call, electronically, or during the study visit. Subjects will also be instructed to contact the research site immediately if their fasting blood glucose is <70 mg/dL or >200 mg/dL, or if their postprandial blood glucose is >400 mg/dL.

After the first 6 weeks, the protocol for home blood glucose monitoring will be made at the discretion of the study site physician. All changes in diabetes medications, based on changes in glycemic control, will be made in conjunction with input from the subject's private physician to ensure medical care is coordinated.

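### Home glucose monitoring of diabetic Control subjects is timed from the start of Aspiration Therapy, which Controls never receive

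*Protocol*

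**What the plan says.** Section 5.3 sets out the Control Group's procedures. For subjects with diabetes it requires a fasting fingerstick every morning and a postprandial one "every evening for the first 6 weeks after starting AT, and report this blood glucose data to the study site every week". It then gives glucose thresholds for contacting the site at once (fasting below 70 or above 200 mg/dL, postprandial above 400 mg/dL). After the six weeks, the site physician decides on further home monitoring.

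Section 3.0 describes the comparator as the "Control Group (Lifestyle Therapy only" arm. Section 5.4.2.3 fixes when AT begins: "Aspiration Therapy starts at the time the Skin-Port is fastened to the A-Tube". That is a device step performed only in the treatment arm.

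Section 5.4.5, for the treatment arm, carries almost the same paragraph, opening "For subjects that have diabetes, subjects will obtain a check (by fingerstick) of their fasting blood glucose every morning" and using the same six-week trigger.

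Section 5.3 does have a clock of its own. For Lifestyle Therapy, "the sessions will be given at week 0, 2, 6, 10, 14, 20, 28, 36, 44, and 52", and for clinic attendance, "The Medical & Study visits occur at weeks 0, 2, 6, 10, 14, 20, 24, 28, 32, 36, 40, 44, 48, and 52". The glucose rule refers to neither.

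**The concern.** This is an operative safety instruction for people with diabetes who are put on an energy-deficit diet: 600 kcal for Controls and 300 kcal for AT subjects (Section 5.5.9). Its start is an event that no Control subject can have. A site that follows the text literally would require no home checks from Controls. A site that infers a start may choose randomization, week 0 or another date. A monitor applying Section 5.7 could not say when a missed check becomes a deviation.

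If sites did read the rule literally, glucose events and changes in diabetes medication could be detected less completely in Controls than in AT subjects. That is a possibility only; nothing in the protocol shows that it would happen.

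**Working it through.** The protocol gives no figure to reproduce here. The check compares sections and then counts what the rule covers.

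**1. Does the paragraph apply to Controls?** It sits in Section 5.3 with no intervening heading and comes before 5.3.1. If home monitoring were meant for AT subjects only, Section 5.4.5 would be enough and 5.3 would not need the paragraph. Controls were therefore meant to monitor.

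**2. Can the trigger occur in Controls?** AT begins with attachment of the Skin-Port (5.4.2.3). Controls receive no A-Tube and no Skin-Port (3.0). The trigger cannot occur, and the later period, which starts after the first six weeks, depends on the same missing date.

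**3. Is a start given elsewhere?** Table 3, the Control schedule, has no row for home glucose monitoring. Control week 0 exists, but nothing links it to this rule.

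**4. Where did the wording come from?** The near-identical text in 5.4.5 points to a carry-over. The pregnancy text was adapted for Controls: 5.5.7 requires stopping AT and removing the A-Tube, whereas 5.3.2 refers only to stopping therapy. The glucose text was not adapted in the same way.

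**5. How much monitoring is undated?**
- Readings: 2 per day × 7 days × 6 weeks = 84 per diabetic Control.
- Reports: 1 per week × 6 weeks = 6 per diabetic Control.

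**6. What else measures glucose early in the Control arm?** From Table 3:

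| Test | Measures glycemia? | Scheduled |
|---|---|---|
| HbA1c | yes | screening, weeks 14, 28, 52 |
| CMP | yes (includes glucose) | screening, weeks 28, 52 |
| Electrolyte panel | no | weeks 2, 6, 10, 14, 20, 36, 44 |

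Scheduled laboratory tests of glucose or HbA1c after screening and before week 14: 0. During Control weeks 0 to 6 the fingersticks are the only glucose measurement specified.

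**The case against.** The strongest reply is that this is a wording slip that any competent site would resolve. Everything else in Section 5.3 runs from week 0, and Table 3 counts weeks of therapy from 0, so for a subject whose therapy is Lifestyle Therapy the first six weeks can sensibly mean only weeks 0 to 6. The contact thresholds and the rule on coordinating diabetes medication with the private physician carry no date, so they stand regardless. The early laboratory gap is not peculiar to Controls: Table 1 gives the AT arm the same HbA1c and CMP weeks. Adverse events and concomitant medications are recorded at every Control visit, including weeks 0, 2 and 6. Eligibility also limits risk, through the exclusion of "Diabetes treated with insulin or sulfonylurea medications", of HbA1c above 9.5%, and of any change in diabetes medication in the previous 3 months.

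All of this is correct, and it limits the weight of the point. It does not remove the error. An inference that sites must make for themselves is not a stated start. The thresholds protect only subjects who are taking readings. In the AT arm the same laboratory gap is covered by home checks with a valid start, which the Control text does not provide. Visit records capture symptoms and drug changes but do not measure glucose.

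**Conclusion.** The point holds: the rule is wrong as written. In the Control arm neither the six-week monitoring period nor the physician-directed period after it has a defined start, which leaves 84 readings and 6 weekly reports per diabetic Control without a date. The protocol does not say how many of the 58 planned Controls would have diabetes, so the number of affected subjects cannot be stated.

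The conclusion rests on the text alone and needs no outside assumption. Its reach is safety monitoring in one subgroup. Sample size, error rates and both primary endpoints are untouched. HbA1c is scheduled in the same weeks in both arms, and Section 8.1.3 limits the secondary endpoints to data tables. The correction should be made, but it does not call the trial's efficacy conclusions into question.

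**What to change.** In Section 5.3, replace the reference to starting AT with Control week 0, the first Lifestyle Therapy session, so that the intensive period is Control weeks 0 to 6 and physician-directed monitoring follows. One added sentence saying that the monitoring and reporting schedule is the same in both arms, each counted from the start of its own therapy, would remove any remaining doubt. It is helpful but not essential once the start is corrected.

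The cost is one phrase in the protocol and a note to sites. No visit, test or subject burden is added beyond what Section 5.3 already intends.

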5.3.1 Retention Plan

Several strategies will be used to enhance adherence with lifestyle intervention and reduce the rate of drop-outs in the Control Group: 1) a philosophy of partnership and collaborative relationships will be encouraged between research site personnel and study participants; 2) reimbursement for time required for study visits will be provided; 3) self-monitoring of dietary intake and physical activity, which will be incorporated into the lifestyle therapy program; 4) Town Hall Meetings will be held for subjects to share experiences and encourage each other, 5) participants will be specifically encouraged to return for key visits that involve outcome measures, so that this data will be captured even in participants who have not regularly attended the other visits, and 6) for participants who, in the opinion of the study team, are losing motivation, one or more meetings with a behavioral

consultant or a successful study participant may be arranged, providing the subject is so willing.

